## 2. 6.3 MEASURES TO MINIMIZE BIAS: RANDOMIZATION AND BLINDING

We will use weighted stratified random assignment. After participants are baselined, we will score their data and assign them a risk tier (low, medium, high). Subsequently, we will randomize them to one of 3 conditions: BE condition, BE + ASIST condition, or control. Since the trial is being conducted in cohorts (waves), and to ensure the least amount of time between being baselined and starting the treatment, participants will be randomized one by one after they are baselined. The weighted component enables there to be equal representation of both risk tier and number of participants across all 3 treatment conditions within the confines of the ongoing nature of the trial.

At the time of baseline, participants are assigned 2 codes: one that is fully numeric, and another that is alphanumeric. The PI and graduate student(s) will have access to the unblinded data (i.e. both the older adults' names, codes, and baseline data) as the PI is supervising the process and a few graduate students will be helping with scoring, and the weighted stratified random assignment. The methodologist will only have access to the participants' codes and raw data. They will remain blind to ensure the most objective analysis of the data.

If a participant remains at elevated risk for suicide at the conclusion of the treatment, we will unblind them and report to their assigned case manager.

We will also use separate documents with participant codes only to track the following: treatment condition, rebaselines, any survey/measurement issues, risk tiers, etc. to ensure an additional level of rigor in protecting against any bias. Further, in all tracking files that the PI's research lab utilizes, only participant IDs will be utilized (i.e. tracking which participants are up for the next measurement occasion, etc.).

The only potential inadvertent unblinding that we could foresee would be with respect to the use of the Friendlybuzz system. The treatment providers do need to know the first names of the older adult participants, therefore ONLY their first names will be available. The data team, however, is completely distinct from the treatment team, and will not have access to the Friendlybuzz system.

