### 1.3 SCHEDULE OF ACTIVITIES

	Week 0	Week 1	Week 2	Week 3	Week 4	Week 5	Week 6	Week 7	Week 8	Week 9
MOUs with AAAs and senior centers	X									
Secure Lists of Potential Participants From Senior Centers	X									
Recruitment Phone Calls		X								
Baseline Survey		X								
Scoring of Baseline Survey		X								
Random Assignment to 3 Conditions		X								
Phone Calls Back to Participants with Corresponding Consent (BE, BE WITH, Control)		X								
Measurement Occasions				X		X		X		X
Call Dosages			X	X	X	X	X	X	X	X

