## 6.1.2 ADMINISTRATION AND/OR DOSING

Sixty trained providers (30 in each treatment condition) will provide the treatment to an assigned caseload of older adults via the phone. We are working with software developers (i.e. Friendlybuzz) who built a system to automatically record the audio files of the treatment dosages. Research team members will populate the caseloads of the older adult clients into Friendlybuzz for the treatment providers which enables the older adults contact information to remain protected (a requirement of our community partners). After caseloads are populated, treatment providers will call into the Friendlybuzz system; treatment providers push “1” for their first older adult, “2” for their second, and so on through their caseloads of 5-7 older adults each.

Treatment providers will not have any interaction with the older adults outside of providing the treatment. Every two weeks, after two call dosages (20-30 minutes each), data will be independently collected from the participants from trained graduate students at Georgia State University. This will go on for an additional 3 measurement occasions, for a total of 4 measurement occasions + the baseline (see graphic below).

Complete participation includes eight full call dosages between the average of 20-30 minutes each. Please see the graphic below for the complete treatment and assessment schedule.

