**Health and Wellbeing**

3. Generalized Anxiety Disorder (GAD-7) measures anxiety.

[https://adaa.org/sites/default/files/GAD-7\\_Anxiety-updated\\_0.pdf](https://adaa.org/sites/default/files/GAD-7_Anxiety-updated_0.pdf)

4. Patient Health Questionnaire (PHQ-9) measures depression.

[https://med.stanford.edu/fastlab/research/imapp/msrs/\\_jcr\\_content/main/accordion/accordion\\_content3/download\\_256324296/file.res/PHQ9%20id%20date%2008.03.pdf](https://med.stanford.edu/fastlab/research/imapp/msrs/_jcr_content/main/accordion/accordion_content3/download_256324296/file.res/PHQ9%20id%20date%2008.03.pdf)

5. Short Form Health Survey (SF-12) measures quality of life.

<https://www.hoagorthopedicinstitute.com/documents/content/SF12form.pdf>

6. Interpersonal Needs Questionnaire (INQ-15) measures suicide desire. The team will be using the thwarted belongingness scale only due to results from previous study.

<https://psy.fsu.edu/~joinerlab/measures/INQ-15.pdf>

7. Session rating scale measures the quality of the therapeutic alliance between a counselor and a client. This scale was adapted from a clinical context to assess the alliance between the older adult client and the volunteer/provider.

<https://www.uvm.edu/~cpincus/Session%20Rating%20Scale.pdf>

Measure	Acronym	What it measures	When to measure	Reliability/ Validity	Number of items	Sponsor (ACL) Category

University of California, Los Angeles Loneliness Scale	UCLA	Loneliness	All time points	Cronbach's alpha: 0.72  Discriminant validity and convergent validity demonstrated	3 items	Category 2: Socialization
Generalized Anxiety Disorder	GAD-7	Anxiety	All time points	Cronbach's alpha: 0.92  Good criterion, construct, factorial and procedural validity demonstrated	7 items	Category 3: Health and Well-being
Patient Health Questionnaire	PHQ-9	Depression	All time points	Cronbach's alpha: 0.89  Good concurrent validity when compared with SRQ-20 (71%, $p < 0.001$ ) and construct validity demonstrated	10 items	Category 3: Health and Well-being
Social Provisions Scale	SPS-5	Social Needs Being Met	All time points	Cronbach's alpha: 0.88  Criterion-related and structural validity demonstrated	5 items	Category 2: Socialization
Short Form Health Survey	SF-12	Quality of Life	All time points	Reliability: test-retest correlation of 0.76 for 12-item Mental Component Summary (MCS)	12 items	Category 3: Health and Well-being

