				Relative validity estimates for 12-item MCS ranged from 0.60 to 1.07 (median = 0.97) in relation to 36-item short-form scale		
Interpersonal Needs Questionnaire	INQ-15	Suicide Desire-thwarted belongingness scale only	All time points	
Reliability: Thwarted Belongingness - Cronbach's alpha: ~ 0.85
 
Good construct validity (thwarted belongingness correlated significantly with loneliness and low social support) and criterion-related validity (thwarted belongingness uniquely predicts current suicidal ideation: odds ratio = 1.59, <math>p < .01</math>)
	15 items (8 TB)	Category 3: Health and Well-being

*\*\*Please review the table below for a summary of the main mental health measures utilized in this PN-RCT.*

Participant screening includes administration of the UCLA, INQ, and SPS, scoring them, and assigning a risk tier. Participants that are middle or high risk will be enrolled in the trial, whereas those that are low risk do not meet eligibility and will be called back to clarify/answer any questions they may have. Measures will be scored the same day, risk tiers and randomization assigned the same day, whereas the call backs to participants may take up to 72 hours.

Trained graduate student data collectors will be administering all assessments via the phone verbally to older adults. Each received training and administered the measure set, was provided with feedback, and made adjustments to ensure that the measures were administered with fidelity across the trial. Further,

there were notations in Qualtrics to indicate reverse coded items, etc., in which wording may be particularly confusing to older adults to remind data collectors to slow down, repeat, and/or rephrase to ensure that the older adult understood each and every item.

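### Section 6.3 treats Friendlybuzz as the one foreseeable unblinding route, yet the plan nowhere masks the interviewers who collect the older-adult questionnaire outcomes to arm, leaving called-versus-control comparisons open to avoidable detection bias.

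*Combined protocol and SAP*

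**What the plan says.** On blinding, section 6.3 says: "The only potential inadvertent unblinding that we could foresee would be with respect to the use of the Friendlybuzz system". It goes on: "The data team, however, is completely distinct from the treatment team, and will not have access to the Friendlybuzz system". The methodologist is to work from codes and raw data. Treatment condition is kept in separate documents that carry codes only, and lab tracking files use IDs. The same section discloses that the principal investigator and graduate students see names, codes and baseline data, since "a few graduate students will be helping with scoring, and the weighted stratified random assignment".

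On outcome collection, section 8.1 says: "Trained graduate student data collectors will be administering all assessments via the phone verbally to older adults". Section 6.1.2 adds that "data will be independently collected from the participants from trained graduate students at Georgia State University". Section 6.1.1 has graduate students give the same measures to controls every two weeks, and section 4.1 says collectors are trained to be conversational. Section 8.1 also describes training with feedback, and Qualtrics notes on confusing items, such as reverse-coded ones, that "remind data collectors to slow down, repeat, and/or rephrase".

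Two further places bear on knowledge of arm. The schedule in section 1.3 lists "Phone Calls Back to Participants with Corresponding Consent (BE, BE WITH, Control" after random assignment; section 10.1.1.2 gives the call-back to an unspecified member of the research team. Section 8.1 includes the Session Rating Scale, adapted to "assess the alliance between the older adult client and the volunteer/provider".

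**The concern.** Participants in this trial cannot be blinded: they either receive weekly calls or do not. The older-adult outcomes are subjective scales of loneliness, belonging, social support, anxiety, depression and quality of life, read aloud by telephone. The interviewer is the one layer between participant and score that could be masked, and the plan does not say that it is.

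An interviewer who knows that someone is being called, and who may repeat or reword an item, can shift the answer without meaning to. The comparator is no calls, so the shift would more plausibly favour the called arms, which is the direction of the hypothesis in section 9.1. A larger sample does not reduce a bias of this kind, and no analysis can be relied on to remove it afterwards.

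**Working it through.** **1. Does any passage mask the interviewers?**

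- Data team distinct from treatment team, without Friendlybuzz access (6.3): separates interviewers from callers, not from knowledge of allocation.
- Codes-only condition files and ID-only tracking (6.3): limit identification, but who may open the condition file is not stated.
- Independent data collection (6.1.2), and call tracking kept apart from measurement tracking (6.4): neither mentions allocation.
- Methodologist working from codes (6.3): concerns analysis, not interviewing.

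None of these is masking to arm.

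**2. Which routes does the text leave open?**

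- *The participant.* Someone who knows whether they are called speaks with an interviewer every two weeks. This needs no inference about staffing.
- *The Session Rating Scale.* Controls have no caller to rate. Section 8.1 has the collectors give all assessments, so using or skipping the scale can separate called from control. It cannot separate BE from BE WITH. The scale is absent from the timing table in 8.1.
- *Staffing.* Graduate students score and randomise, graduate students interview, and a research team member makes the arm-specific call-back. The text neither says that these people interview the same participants nor prevents it.

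**3. Which outcomes are exposed?** The interview scales in 8.1, which include the primary endpoints of 9.1. The SIRI-2 and Empathy scale (9.4.3) are completed by helpers, and coded calls (sections 3 and 9.4.9) come from recordings, so these are not affected.

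**4. The plan's own sample size, reproduced first.** Inputs from 9.2: effect .40, Type I error .05 (taken as two-sided), power .80, ICC .20, R² .50, 6 older adults per caller. I assume total SD 1 and R² of .50 at both levels; 9.2 does not give the level.

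Variance of a called-minus-control difference = (1 − R²)[1 + (m − 1)ICC]/n(called) + (1 − R²)/n(control), with m the number per caller.

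- With m = 6, 1 + 5 × 0.20 = 2.
- With 90 per arm: 0.5 × 2/90 + 0.5/90 = 0.01667, so SE = 0.129.
- Power from the noncentral t on 14 df (15 callers per arm less 1) is 0.82. With 14 callers per arm it is 0.79.
- So 15 callers per arm, 3 × 90 = 270 in all, as stated.

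**5. Illustration at the planned size.** With 180 per arm: 0.5 × 2/180 + 0.5/180 = 0.00833, so SE = 0.0913 SD. With no true effect and an assumed interviewer bias b, a two-sided test rejects with probability Φ(b/SE − z) + Φ(−b/SE − z), where z is 1.96 at .05 and 2.576 at .01 (the level named in 9.4.1).

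| Assumed b (SD) | b/SE | Rejects at .05 | Rejects at .01 |
|---|---|---|---|
| 0 | 0 | 5% | 1% |
| 0.05 | 0.548 | 8.5% | 2.2% |
| 0.10 | 1.095 | 19.5% | 7.0% |
| 0.20 | 2.191 | 59.1% | 35.0% |

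Sensitivity at b = 0.10: a t reference on 29 df gives 18.5% and 6.2%. With R² at the participant level only, the variance is (0.20 × 6 + 0.80 × 0.5)/180 + 0.5/180 = 0.01167, SE = 0.108, and the rates are about 15% and 5%.

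**The case against.** The strongest reply is that the Friendlybuzz sentence may not be about arm at all. It speaks of inadvertent unblinding. Section 6.3 uses unblinding language for identity elsewhere, and the sentence leads into limiting callers to first names. The access of students who randomise is disclosed openly in the same section. This stands as a reading of the sentence, but it leaves the gap unchanged: if 6.3 concerns identity, the plan says still less about masking interviewers to arm.

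Four stronger readings are tempting, and the documents do not support them.

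- *The randomising students or call-back staff also conduct the interviews.* The text only fails to exclude it.
- *Every trial outcome is exposed.* The helper measures and coded calls are not.
- *Interviewers may reword at will.* The notes are tied to confusing items and follow training and feedback aimed at uniform administration. Still, their stated aim extends to every item, and no approved wordings are given.
- *No script or scale order exists.* The text at hand shows none, but the appendix with the battery and the schedule graphic are not part of it, so this cannot be asserted.

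The bias sizes are assumptions, and the table shows only how sensitive the test is to them. Masking interviewers also leaves bias in the participants' own unmasked self-report; the fix addresses only the interviewer's part.

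**Conclusion.** The point holds in limited form. The plan does not mask outcome interviewers to arm, and Friendlybuzz is not the only foreseeable way for them to learn it. The participant route alone shows this, and the Session Rating Scale adds a second. Staff overlap is a missing safeguard, not a documented practice. The older-adult interview outcomes are exposed in called-versus-control comparisons.

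The actual size of the bias is unknown. If it were 0.10 SD, a quarter of the design effect of .40, a test with no true effect would reject about 20% of the time at .05 and about 7% at .01. These rates rest on the assumed bias, 180 per arm, 6 per caller, ICC .20, R² of .50 at both levels and a normal approximation; the alternatives checked lower them to about 15% and 5%. The change is worth making because it is cheap and protects the primary endpoints.

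**What to change.** In section 6.3, replace the Friendlybuzz sentence with a rule that outcome interviewers are masked to arm:

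- (a) Anyone who scores, randomises, makes the condition call-back or holds the condition file for a participant does not collect that participant's post-baseline outcomes.
- (b) Each outcome call opens with a scripted request not to mention whether calls are being received.
- (c) The Session Rating Scale is given last, after the outcome scales have been entered and locked in Qualtrics.
- (d) In section 8.1, rephrasing is limited to fixed alternative wordings held in Qualtrics.
- (e) After each call the interviewer records whether the arm was revealed, for a sensitivity analysis. Disclosure will itself depend on arm, so this analysis describes the problem and does not correct it.

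State as a limitation that participants' self-report remains unmasked.

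The cost is protocol wording, a reordered survey and a rota that divides students by role, with less scheduling flexibility for the on-call collectors. It should need no added visits. The documents do not give the number of students, so the sponsor should confirm that the rota can be staffed.

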## 3. 6.4 STUDY INTERVENTION/EXPERIMENTAL MANIPULATION ADHERENCE

Participants' adherence to the study procedures will be tracked in two ways: (1) through the Friendlybuzz system (tracking adherence to the treatment), and (2) through lab tracking documents (adherence to the measurement, data collection). The Friendlybuzz system will allow us to track in real time the call dosages as they are coming in, the duration of those, timing, etc. The lab tracking documents will enable us to know which participants need the next measurement occasion for data collection. These two

processes remain separate and distinct, to ensure that the treatment is distinct from the measurement of the treatment.

Treatment providers are required to complete training a priori, and utilize the documents and tools (i.e. guidelines for making sincere connections, reminiscence table whereby there are questions provided in each area of the older adults life for the treatment provider to track and follow up on in subsequent sessions, etc.) provided to them to deliver 8 high quality treatment dosages to their caseload of older adult participants that are 20-30 minutes in duration each. They are required to track that, as well as attend weekly supervision and check in with a supervisor who is tracking their treatment delivery through the Friendlybuzz system.

Participants are required to complete a “participation plan” which will be mailed to them after they are baselined, meet eligibility criteria and are randomized. Those randomized to one of the two treatment conditions are required to participate in 8 call dosages and 4 additional measurement occasions. Those randomized to the control group are required to participate in 4 additional measurement occasions and provided with the option to receive 8 call dosages 2 months later (delayed waitlist control).

#### 4. 6.5 CONCOMITANT THERAPY

N/A

##### 1. 6.5.1 RESCUE THERAPY

N/A

### 9. 7 STUDY INTERVENTION/EXPERIMENTAL MANIPULATION DISCONTINUATION AND PARTICIPANT DISCONTINUATION/WITHDRAWAL

#### 1. 7.1 DISCONTINUATION OF STUDY INTERVENTION/EXPERIMENTAL MANIPULATION

Since this study involves older adults there may be death which would result in the participants' inability to continue the study.

#### 2. 7.2 PARTICIPANT DISCONTINUATION/WITHDRAWAL FROM THE STUDY

Participants may withdraw voluntarily from the study at any time, and/or the PI may discontinue a participant from the study if the participant has cognitive impairment and has somehow not been excluded previously. The rationale includes (a) limited/incorrect data being collected from any participant with cognitive impairment, and (b) may be potentially distressing to participants with cognitive impairment. The only reason this is included here is in the very slight chance that a participant with cognitive

impairment gets through the screening processes we have in place, PIs have the obligation to remove them from the study.

We will have ongoing contacts with older adult participants throughout the 8-week study. We anticipate low attrition due to weekly doses being provided by the ASN providers we train and supervise to provide the treatment as well as every other week data collection by trained graduate students. During supervision meetings with both those trained providing the treatment, as well as those collecting the data, any challenges will be discussed and addressed. Data collectors have an “on call” schedule in which at all times there are 2 members of the PI’s lab that will be tracking data and data needs. In addition, daily tracking will occur by the grant coordinator who will post any missing data through de-identified participant ID codes in a shared GroupMe with the trained data collectors to ensure that those “on call” can collect that data in real time.

Any participant that chose to withdraw will be supported for their choice. We anticipate that older adults may have health issues, hospitalizations, and/or various other serious adverse events in their lives and we will ensure the tracking of these for attrition reasons. The data to be collected at the time of study discontinuation will include the following:

- The reason(s) for discontinuing the participant from the intervention (for attrition tracking)
- If the participant is due to complete assessments and whether or not those assessments will be administered at the time of discontinuation

For any participants that discontinues due to a health issue, hospitalization or otherwise and wishes to continue treatment, we will offer to re-baseline them and re-enroll them in a subsequent wave of treatment to ensure that the challenge that existed in their life does not keep them from being able to participate.

### 3. 7.3 LOST TO FOLLOW-UP

The following actions must be taken if a participant fails to answer the phone with attempts to administer treatment and collect data:

- We will attempt to contact the participant, reschedule the missed survey or call with the trained helper within the next 72 hours and ascertain if the participant wishes to and/or should continue in the study.
- Before a participant is deemed lost to follow-up, the investigator or designee will make every effort to regain contact with the participant (where possible, 3 telephone calls or reach out to the designated senior center case manager). These contact attempts will be documented in the participant’s study file.
- Should the participant continue to be unreachable, he or she will be considered to have withdrawn from the study with a primary reason of lost to follow-up.

As far as any missing data that may result, we are utilizing the Intent to Treat (ITT) approach therefore all data from any participants lost to follow-up will be included, and data not collected left blank in the longitudinal multilevel modeling analysis.

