### 3. 9.3 POPULATIONS FOR ANALYSES

The population for analysis includes all randomized participants who met inclusion criteria. We are using the Intention-to-Treat (ITT) Approach, meaning that even those participants that had an AE or dropped out of the treatment will still be included.

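### Sections 7.1 to 7.3 do not separate stopping the calls from leaving the study, so week-8 outcomes for the intention-to-treat analysis are not secured

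*Combined protocol and SAP*

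**What the plan says.** Section 7.1, on stopping the intervention, says only that "there may be death which would result in the participants' inability to continue the study". It does not cover a participant who no longer takes calls but could still be surveyed.

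Section 7.2 lists what is recorded when someone leaves the study. One item is the reason for leaving the intervention. The other is "If the participant is due to complete assessments and whether or not those assessments will be administered at the time of discontinuation". Later occasions are not mentioned. A participant who stops for health reasons and wants to go on may be re-baselined in a later wave. Section 6.2.1 has a similar restart for participants whose provider can no longer call them.

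Section 7.3 opens with "The following actions must be taken if a participant fails to answer the phone with attempts to administer treatment and collect data". Staff are to "reschedule the missed survey or call with the trained helper within the next 72 hours" and ask whether the person wants to, or should, stay in the study. After further contact attempts the rule ends: "Should the participant continue to be unreachable, he or she will be considered to have withdrawn from the study". Data already collected are kept, and the rest is left blank in the longitudinal model.

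Section 9.3 defines the population by intention to treat: "even those participants that had an AE or dropped out of the treatment will still be included". Section 6.1.2 describes the survey rhythm: "Every two weeks, after two call dosages (20-30 minutes each), data will be independently collected". Graduate students, not the callers, do the surveys. Section 6.1.1 gives all three conditions the same outcome intervals, and 6.4 keeps the tracking of calls apart from the tracking of measurements.

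**The concern.** An intention-to-treat comparison needs outcomes after treatment stops as well as a rule that everyone is counted. Section 9.3 supplies the rule, but 7.1 to 7.3 do not supply the data. A called participant who gives up the calls halfway could be surveyed to week 8 or could be treated as having left, and staff could follow either course without breaking the protocol.

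Only the BE and BE WITH arms have calls to stop during the eight weeks, so loss of this kind can differ between the called arms and control. Where later values are blank, a longitudinal model in effect assumes that stoppers would have continued like comparable people still being called. The estimate then moves towards the effect had everyone kept taking calls, which is not the effect that 9.3 claims. No sensitivity analysis for missing participant outcomes is described; multiple imputation appears only in 9.4.3, for the helpers' measures.

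**Working it through.** **Step 1. Is a survey due after calls stop?** Take a participant who stops calls after treatment week 4 and ask whether the week-6 and week-8 surveys take place.

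- 7.1: no answer, since only death is named.
- 7.2: it merges the two events, because a reason for leaving the intervention is recorded at departure from the study. It covers an assessment due at that moment, leaves open even whether that one is given, and says nothing of later ones.
- 7.3: a reachable person has the missed contact rescheduled. A persistently unreachable person is withdrawn, and no attempt at later occasions is stated.
- 1.3, 4.1 and 6.1.1: surveys follow a two-weekly calendar, the same in all arms. This sets the planned schedule but does not address people who have stopped.
- 6.3 and 6.4: the data team has no access to the call system, and measurement is tracked separately. This concerns tracking, not whether follow-up continues.
- 9.3: this says who is analysed, not whether their outcomes are obtained.

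Several passages are consistent with continued surveys; none requires them.

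**Step 2. The plan's own sample size.** Section 9.2 gives effect 0.40, alpha .05, power .80, ICC .20, R² .50, 6 older adults per volunteer, and 270 in total (90 per arm). For one called arm against control, assuming a two-sided test and R² acting at both levels:

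Var = (1 − R²) × [(1 + (m − 1) × ICC)/n + 1/n] = 0.50 × [(1 + 5 × 0.20)/90 + 1/90] = 0.50 × 3/90 = 0.0167

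The SE is 0.129 and 0.40/0.129 = 3.10. A noncentral t with 15 − 1 = 14 df gives power 0.821, and 90 is the smallest arm size that reaches 0.80. The 270 reproduces. It contains no stopping rate, so this point leaves it unchanged.

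**Step 3. Range for the share who stop.** The documents give no rate. Section 5.5 adds at least 200 to 540, and 200/740 = 27%. That allowance covers attrition of every kind, so 27% serves only as an upper scenario beside assumed values of 10% and 20%.

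**Step 4. Illustration.** Assume that benefit grows linearly to 0.40 SD at week 8 (0.20 at week 4), that a share p of the called arm stops after week 4 and is not surveyed again, and that stoppers resemble the others until then. The observed data cannot then distinguish stoppers from stayers, so the model estimate is about 0.40. With e the stoppers' own week-8 effect:

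true effect = (1 − p) × 0.40 + p × e; relative error = 0.40/true − 1

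| After stopping | e | p = 10% | p = 20% | p = 27% |
|---|---|---|---|---|
| All benefit lost | 0 | 0.36 (+11%) | 0.32 (+25%) | 0.29 (+37%) |
| Benefit frozen at week 4 | 0.20 | 0.38 (+5%) | 0.36 (+11%) | 0.35 (+16%) |
| Same course | 0.40 | 0.40 (0) | 0.40 (0) | 0.40 (0) |
| 1.5 times the benefit | 0.60 | 0.42 (−5%) | 0.44 (−9%) | 0.45 (−12%) |

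Percentages use unrounded true effects.

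A simulation with 150,000 per arm, five occasions, an assumed within-person correlation of 0.6, a likelihood repeated-measures model and no helper clustering agrees. Its estimates lay between 0.396 and 0.405 in all twelve cells, and its true effects were within 0.01 of the table.

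**The case against.** The best defence is that the plan already points to continued surveys. Outcome collection is independent of the callers, runs on a common calendar, is tracked apart from the calls, and is backed in 7.2 by daily checks for missing data and on-call collectors. This rules out four stronger readings.

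- A reader might infer from 7.3 that stopping calls means leaving the study. It does not say so. Withdrawal there needs continued unreachability, and a person who declines the helper but answers the graduate student is reachable.
- A reader might infer from 6.1.2 that each survey waits for two completed calls. Sections 1.3, 4.1 and 6.1.1 set surveys by calendar, so the phrase reads as a description of the schedule.
- A reader might compare 8 + 4 = 12 contacts in a called arm with 4 in control and see a threefold risk of withdrawal. Contacts are not risks. One missed contact withdraws nobody, more contacts also give more chances to reach someone, and 7.2 expects the weekly calls to lower attrition.
- A reader might infer that the treatment effect is necessarily overstated. The table shows that the sign depends on how stoppers fare. The health problems and hospital stays anticipated in 7.2 make worse outcomes plausible, but nothing in the documents establishes them.

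What the defence does not supply is a sentence committing to the remaining surveys. It is also true that better wording cannot produce data from someone who stays out of reach, which is why a sensitivity analysis is needed too.

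**Conclusion.** The gap is real, but it is an unspecified rule and not a rule that ends follow-up. Sections 7.1 to 7.3 leave open whether surveys continue after calls stop, so the intention-to-treat claim is not secured by the data collection plan.

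Neither the size nor the sign of any bias can be computed from the documents. Under the assumptions above it runs from about 12% understatement to 37% overstatement of a 0.40 SD effect. Surveying stoppers to week 8 removes this source of bias. The point merits action because outcomes never collected cannot be recovered at analysis, whereas the surveys and the staff to do them are already planned.

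**What to change.** These changes concern outcome collection and analysis only, not when calls should stop.

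- In 7.2 and 7.3, state that stopping or missing calls is not withdrawal from the study.
- Keep attempting every remaining scheduled survey, on the same calendar in all three arms, unless the participant declines surveys.
- State that a missed occasion or a spell of being unreachable does not cancel later attempts.
- Record the date of the last call and the date of the last survey as separate fields.
- For anyone re-baselined or re-enrolled (6.2.1, 7.2), keep the original randomised assignment, baseline and survey series as the primary data.
- Add a sensitivity analysis, for example control-based imputation, for outcomes still missing after calls stop.
- In 6.1.2, align the wording with the common calendar in 6.1.1; nothing more is needed there.

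The cost is protocol wording, two date fields, one added analysis and a little more data-collector time. The estimated effect may turn out somewhat smaller.
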